5.0 Statistical Considerations

5.1. Hypotheses.

Aim 1. We hypothesize that the majority of providers, patients and parents will express positive views about the PREVENT tool and its sustained use in clinical settings.

Aim 2. We hypothesize that patients who receive PREVENT will have greater improvements in attitudes toward behavior change recommendations, adherence to recommended behavior change and CVH compared to those who did not receive PREVENT during their clinic visit.

5.2. Data Analysis Plan

Statistical analysis will be performed using SAS v9.4 (quantitative data) and NVivo12 software (qualitative data).

For our Aim 1 hypothesis, analyses will be largely descriptive (using means, medians and frequencies) for adoption, implementation and maintenance outcomes using survey and observation data. Aim 1 will also be tested using qualitative data. In-depth interview and observation data will be professionally transcribed, anonymized, and imported into NVivo10 software for thematic analysis. The following steps will be performed for indepth interviews and observation data. Guides will be developed and piloted. Coders (n=2) will read over all transcripts and develop a draft of the coding tool. We will practice coding at least three transcripts together to make sure all concepts are adequately captured in the tool. Once the tool is finalized, coders will be assigned transcripts for coding, ensuring each one will be coded by at least two people for reliability and decreased positionality bias. We will summarize codes into general themes and highlight main findings with quotes.

Our Aim 2 hypothesis will be tested using EHR data, accelerometry and patient survey data. Accelerometry data will be processed and analyzed using Actigraph software and SAS v9.4 using protocols validated in adolescents. The participants' demographics and anthropometrics will be summarized using mean and standard deviation by treatment groups. The differences of factors of interest (physical activity, dietary intake, and CVH risk factors) between the 2 study groups at baseline will be compared using linear regressions. Change from baseline between study groups will be tested using linear regressions. Statistical significance will be defined as p<0.05.

Ultimately, Aim 1 and Aim 2 quantitative and qualitative data will be integrated to determine overall feasibility, revise the PREVENT tool and identify barriers to current and future implementation that will inform an implementation strategy for the larger trial.

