2.0 Summary of Study Plan

Fifty adolescents aged 12 to 19 years at risk for poor CVH (BMI \geq 85th percentile) will be recruited over a 9-month period (**Table 1**) from the Late Effects Clinic and randomized to intervention or wait-list control (**Figure 1**). Provider's and patient's perceptions of barriers to implementation and maintenance of PREVENT (*e.g.*, usability, acceptability, motivation for use, workflow compatibility) will be

Year	1		2					
Quarter	1	2	3	4	1	2	3	4
Recruit Advisory Board								
Develop Manual of Procedures								
IRB Approval								
Train Study Staff								
Advisory Board Bi-Annually								
Recruit								
PREVENT Feasibility Study								
Data Analysis								
Manuscript Development								
Refine PREVENT Tool								
R01 Submission								

examined using: 1) surveys administered to all providers at clinic; 2) semi-structured interviews with 5-10 diverse providers (*e.g.*, physicians, nurses, clinic staff, clinical research associates); and 3) two focus groups, one with patients (n=10) and one with parents (n=10) (**Aim 1**). These evaluations will be guided by RE-AIM³³ and administered following the intervention period. Implementation (*e.g.*, intervention delivery, fidelity, time

FOR IRB USE ONLY \$STAMP_IRB_ID \$STAMP_APPRV_DT \$STAMP_REL_DT \$STAMP_EXP_DT

of use) will be examined using direct observation and audio recordings of 15 providerpatient interactions while using PREVENT. Patient attitudes toward behavior change recommendations and risk factors (BMI z-score, cholesterol, blood pressure, physical activity and food intake) will be measured using surveys, physical activity tracking devices (accelerometers) and EHR-data extraction at baseline and 3-months (**Aim 2**). An advisory board will be established and meet bi-annually to provide adolescent (n=5), parent (n=5) and provider (n=5) perspectives on study implementation and inform revisions to PREVENT.

Key dates (Table 1).

- Provider training: October 2020-January 2021
- Patient recruitment: February 2021- April 2021
- PREVENT feasibility study: January 2021-September 2021

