4.2 Enrollment and Consent

4.2.1 Patient enrollment. If patient is interested, the consent form will be reviewed over the phone. Adequate time will be allotted to allow the patient to ask any questions. Additionally, the patient may use the contact information provided on the consent document to follow-up with additional questions prior to completing the consent. If the patient is 18 years or younger, we will ensure that the parent is on the phone while we review the consent document. If the parent is not available, we will call back to discuss the consent form. Following this conversation, an electronic consent (developed in REDCap with guidance from the ICTS mHealth Research Core) will be emailed. The study team will send a test email in a secure manner (i.e., [secure] in subject line) prior to sending consent to verify the participant's identify. The email will instruct the participant to send all information as a response to this thread and not to remove the "[secure]" from the subject line. All future email correspondence will follow this protocol. If the patient is 18 years or younger, the parent and patient will be required to complete the consent document. If the patient is at least 19 years of age, the parent is not required to provide consent. If the patient does not have access to complete an electronic form, a consent will be mailed with a return envelope to receive written consent. Postage costs will be covered by the study. Once consent is obtained, the patient will received an emailed or hard copy of the signed document. Following consent, the patient will complete baseline measures (questionnaires administered electronically or by mail; accelerometers administered by mail). Following baseline measurement, patients will be randomized to intervention or wait-list control and attend their clinic visit. The study staff will call the participant one-week before their clinic visit to remind them of their appointment time, give them details about the appointment and address any barriers they may be facing to complete baseline measurements. Follow-up

St.Louis Washington University in St.Louis

FOR IRB USE ONLY \$STAMP_IRB_ID \$STAMP_APPRV_DT \$STAMP_REL_DT \$STAMP_EXP_DT

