Wait-list control. Patients will attend a routine care visit in-person or remotely. A PREVENT action plan (behavior change prescription, community resources and education) will provided to the patient via email after the completion of follow-up measurement.

Follow-up measurement. Immediately following the clinic visit (within 48 hours) all patients will be sent electronically a brief 10-question (yes/no) survey regarding their clinical interaction. Participants randomized to intervention will also receive questions about their satisfaction with the

FOR IRB USE ONLY \$STAMP_IRB_ID \$STAMP_APPRV_DT \$STAMP_REL_DT \$STAMP_EXP_DT

PREVENT tool. Three months after the patient's clinic visit, they will be sent the Health Behavior & Attitudes Survey electronically and an accelerometer via mail. Only patients who presented with abnormal values for CVH risk factors will return to the Late Effects Clinic to complete a routine clinic visit in accordance with the standard of care for these high-risk patients. Study staff will extract the most-recent EHR data for CVH risk factors for all patients.

Qualitative data collection. Semi-structured interviews will be completed within one month of the completion of follow-up measurement for all participants that received the PREVENT tool.

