4.4 Data Collection Methods

Theoretical underpinnings. This feasibility study will apply principles of Designing for Dissemination, Implementation and Sustainability (D4DIS) to understand factors critical to external validity and refine the existing PREVENT tool to fit well with provider's and patient's needs, assets and timeframes.³⁹ We seek to speed translation of the PREVENT tool into practice by simultaneously collecting mixed method data regarding determinants of current and future implementation of the PREVENT tool, guided by the new Reach, Efficacy, Adoption, Implementation, and Maintenance (RE-AIM) framework.^{40,41} The updated RE-AIM framework will be used to identify barriers to implementation and dissemination as outlined in **Table 3**.

RE-AIM Construct	Measure	Data Source	Stakeholder
Reach	Representativeness compared to eligible clinic population	EHR data; Demographics survey	Patients
Efficacy	Changes in health behaviors and attitudes; Change in CVH risk factors	Health Behavior & Attitudes Survey; accelerometry; EHR data	Patients
Adoption	Usability; acceptability; consistency with priorities/values	Patient and parent interviews; Provider survey	Patient, parent, provider
Implementation	Intervention delivery; fidelity to the protocol; time of PREVENT use; compatibility with workflow	Direct observation, audio recordings of implementation	Patient
Maintenance	Barriers and enabling factors for continued implementation of PREVENT	Qualitative interviews; Provider survey; Clinical Sustainability Assessment Tool	Provider

Table 3: RE-AIM Outcome Measures

4.4.1 EHR data extraction. Patient demographics (e.g., sex, date of birth, race/ethnicity) and the most recent risk factors for CVH (height, weight, fasting blood glucose, total cholesterol, blood pressure, smoking status) will be extracted at baseline (prior to clinic visit) and at follow-up (3-months). Available EHR data will be uploaded into PREVENT prior to the clinic visit but may be updated within the PREVENT tool at the time of the clinic visit if updated values are attained. CVH risk factor data within the tool at the time of the clinic will be used as baseline values and used to determine changes from baseline to follow-up. Only patients with abnormal baseline values will return for a follow-up clinic visit at 3-months. Therefore, we acknowledge that not all patients will have updated

FOR IRB USE ONLY \$STAMP_IRB_ID \$STAMP_APPRV_DT \$STAMP_REL_DT \$STAMP_EXP_DT

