4.4.4 Accelerometers will be administered to patients at baseline and 6-month follow-up to objectively measure levels of physical activity (light, moderate, vigorous) and sedentary behaviors. At baseline, accelerometers will be mailed to participants after consent is obtained and returned by mail using a provided prepaid envelop or at the clinic visit. The following materials will be sent via mail with the accelerometer device: a pre-paid return envelope, a welcome letter, and directions for use. Participants randomized to the intervention group will also receive a document detailing "what to expect" at their clinic visit. At follow-up, accelerometers will be mailed including a pre-paid return envelope. Participants will be asked to wear the device for 7 days including 2 weekend days on a belt (provided) around their waist. Participants will be instructed to remove the device only when bathing or swimming; they will continue to wear the device while sleeping.

4.4.5 Patient and parent qualitative interviews will examine facilitators and barriers to *maintenance*. Semi-structured interviews will be conducted individually with patients (n=10) and parents (n=10). Questions will assess satisfaction with their provider interaction, the PREVENT tool's design, physical activity and nutrition prescriptions, community resources (*e.g.*, are there other resources that would be helpful, did these resources help you or your child achieve the goals)

FOR IRB USE ONLY \$STAMP_IRB_ID \$STAMP_APPRV_DT \$STAMP_REL_DT \$STAMP_EXP_DT

and, more generally, other ways the clinic may help them achieve behavior change.

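### Section 5.2 names no covariate for the Aim 2 change-from-baseline regressions; adding each survey or accelerometer outcome's own baseline would usually narrow the interval and costs one degree of freedom

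*Combined protocol and SAP*

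**What the plan says.** Section 5.2 gives the Aim 2 test in one sentence, "Change from baseline between study groups will be tested using linear regressions", with significance at p<0.05. Neither that section nor any other names a covariate. The sentence before it compares the groups at baseline, also by linear regression. That is a separate comparison, not an adjustment of the change model.

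Section 2.0 says that attitudes and risk factors "will be measured using surveys, physical activity tracking devices (accelerometers) and EHR-data extraction at baseline and 3-months". Section 4.4.3 collects the Health Behavior & Attitudes Survey at baseline and follow-up, and section 4.4.4 does the same for accelerometry. Section 4.2.1 puts baseline ahead of allocation: "Following baseline measurement, patients will be randomized to intervention or wait-list control and attend their clinic visit".

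Two statements about the accelerometer do not fit together:

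- **Follow-up time.** Section 4.3.1 has patients contacted three months after the visit, when "they will be sent the Health Behavior & Attitudes Survey electronically and an accelerometer via mail". Sections 2.0 and 4.2.1 also use three months. Section 4.4.4 says "Accelerometers will be administered to patients at baseline and 6-month follow-up".
- **Order of events.** Right after listing the contents of the baseline accelerometer mailing, section 4.4.4 adds "Participants randomized to the intervention group will also receive a document detailing" what to expect at the visit. That presupposes a known allocation, while section 4.2.1 randomises after baseline.

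EHR risk factors are handled differently. Section 4.4.1 says "CVH risk factor data within the tool at the time of the clinic will be used as baseline values", and "Only patients with abnormal baseline values will return for a follow-up clinic visit at 3-months".

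**The concern.** The sentence in section 5.2 can be read as group alone or as group plus baseline. These are different models, with different estimates and intervals, and the plan does not say which applies.

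A group-only analysis of change subtracts the whole baseline value, in effect fixing its slope at 1. When the true slope is below 1, this over-corrects and adds noise. In any one trial, the estimate is also shifted by whatever baseline imbalance chance has produced. Estimating the slope from the data removes most of this.

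What is at stake is the width of the intervals for survey and accelerometer outcomes in 50 patients, whose results are meant to inform a larger trial. Error control is not at stake.

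**Working it through.** The plan states no power, effect size, SD or correlation, so there is no design figure to reproduce.

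**Inputs from the documents:** N = 50 (section 2.0) and p<0.05 (section 5.2).

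**Assumptions:** two-sided testing, 1:1 allocation, 50 complete pairs, rho from 0.4 to 0.9, and k = follow-up SD / baseline SD of 0.8, 1 or 1.25.

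**Formulas**, per patient, in units of baseline variance:

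- Change score: Vc = 1 + k² − 2·rho·k
- Baseline-adjusted: Va = k²(1 − rho²) × [1 + 1/(N − 4)]. The bracket charges for estimating the slope; at N = 50 it is 47/46 = 1.0217.

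**Equal SDs (k = 1).** The ratio Va/Vc reduces to (1 + rho)/2 × 47/46.

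| rho | Vc | Va | Va/Vc | Variance change | 95% CI half-width (SD), change → adjusted |
|---|---|---|---|---|---|
| 0.4 | 1.20 | 0.84 × 1.0217 = 0.858 | 0.715 | −28% | 0.62 → 0.53 |
| 0.6 | 0.80 | 0.64 × 1.0217 = 0.654 | 0.817 | −18% | 0.51 → 0.46 |
| 0.8 | 0.40 | 0.36 × 1.0217 = 0.368 | 0.920 | −8% | 0.36 → 0.35 |
| 0.9 | 0.20 | 0.19 × 1.0217 = 0.194 | 0.971 | −3% | 0.25 → 0.25 |

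The half-width is t(0.975, df) × √(V × 4/50), with df 48 for change and 47 for adjusted. The effect detectable with 80% power (noncentral t) goes from 0.89 to 0.75 SD at rho 0.4 and from 0.72 to 0.65 SD at rho 0.6. With equal SDs the gain reaches zero at rho = 2/1.0217 − 1 = 0.957.

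Simulation with 40,000 null trials per rho agreed: the variance ratios were 0.716, 0.821, 0.916 and 0.972 at these four values. Overall type I error was 0.049 to 0.053 for the change score and 0.049 to 0.051 for the adjusted model.

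**Unequal SDs, N = 50.**

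| rho | k = 1.25: Vc, Va | Variance change | k = 0.8: Vc, Va | Variance change |
|---|---|---|---|---|
| 0.4 | 1.5625, 1.341 | −14% | 1.00, 0.549 | −45% |
| 0.6 | 1.0625, 1.022 | −4% | 0.68, 0.419 | −38% |
| 0.8 | 0.5625, 0.575 | +2% | 0.36, 0.235 | −35% |
| 0.9 | 0.3125, 0.303 | −3% | 0.20, 0.124 | −38% |

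**Limit on the loss.** Before the degree-of-freedom charge, Vc − Va = (1 − rho·k)², which is never negative. It is zero when rho·k = 1, as at rho 0.8 and k = 1.25. The loss under this formula therefore cannot exceed 1/(N − 4): 2.2% at N = 50, 2.8% at N = 40 and 3.8% at N = 30.

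**Fewer complete pairs, equal SDs.** At rho 0.4, 0.6, 0.8 and 0.9 the falls are 28%, 18%, 7.5% and 2.4% at N = 40, and 27%, 17%, 6.5% and 1.3% at N = 30.

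**Chance imbalance, equal SDs.** A baseline difference of one standard error, √(2/25) = 0.28 SD, shifts the group-only change estimate by (1 − 0.4) × 0.28 = 0.17 SD at rho 0.4.

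**The case against.** **The plan does not say group only.** This stands. If a baseline term is already intended, nothing is lost but a phrase, and every figure above is conditional on the group-only reading.

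**The equal-SD range is not a bound.** This also stands. A reader might take 28% to 3% as the limits of the gain. The documents give no SDs, and at k = 1.25 and rho 0.8 there is a small loss. What survives is the asymmetry: at worst about 2% of variance at N = 50, against a possible gain many times larger.

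**Some surveys have no baseline value.** The post-visit yes/no survey, the satisfaction questions and the 4-, 8- and 12-week check-ins cannot be adjusted in this way. The point is confined to the Health Behavior & Attitudes Survey and accelerometry.

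**BMI, the named primary health outcome, is left out.** This is deliberate. The EHR baseline may be updated at the visit, after randomisation, and return at three months is selective. A baseline covariate cures neither. If rho for BMI were 0.95 (assumed), the ratio at N = 50 would be 0.975 × 1.0217 = 0.996, which is essentially no gain.

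**The accelerometer baseline is itself unsettled.** Section 4.4.4 does not say outright that the intervention document travels in the baseline parcel, so the conflict is one of implication. A reader might infer that adjustment protects against a baseline measured after allocation. That holds only if follow-up is unaffected: a 0.2 SD baseline shift at rho 0.4 then biases the change score by 0.20 SD and the adjusted estimate by 0.4 × 0.2 = 0.08 SD. If the same shift persisted at follow-up, the change score would be unbiased and the adjusted estimate off by 0.6 × 0.2 = 0.12 SD. The order of events has to be settled in the text.

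**Conclusion.** The point holds as a minor one. Section 5.2 leaves the Aim 2 model under-specified. For the Health Behavior & Attitudes Survey and accelerometry, including the outcome's own baseline is the better default. The size rests on assumed rho, SD ratio, 1:1 allocation and complete pairs, none of which the documents give.

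A reader might infer that the planned test is biased or has inflated type I error. The documents do not support that: under randomisation with a pre-allocation baseline, the group-only change test is valid overall. A reader might also infer that the study is underpowered because of this choice. It is a feasibility study that states no power, so there is no target to miss.

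The two accelerometer conflicts affect adjusted and unadjusted analyses alike. They add no weight to this point, but until they are settled the accelerometer's baseline and follow-up do not each have a single meaning.

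**What to change.** In section 5.2, add:

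*For each Health Behavior & Attitudes Survey and accelerometer outcome measured at baseline and follow-up, the follow-up value (or change) will be regressed on randomised group and the baseline value of that outcome; the adjusted group difference and 95% CI will be reported.*

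With the baseline in the model, follow-up value and change give the same group estimate, so either may be used. The sentence is not proposed for EHR outcomes or for surveys without a baseline value.

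Separately, reconcile the accelerometer follow-up time in section 4.4.4 with sections 2.0, 4.2.1 and 4.3.1. Also reconcile the intervention-only document in section 4.4.4 with randomisation after baseline in section 4.2.1, so that the accelerometer covariate is clearly measured before randomisation.

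The cost is one sentence, one model term in SAS and one degree of freedom, with no new data. The reconciliations are text edits.

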information for CVH risk factors (BMI, fasting blood glucose, total cholesterol and blood pressure) from baseline). This feasibility study is intended to determine what data are commonly available for a future study. We expect that height and weight will be the most commonly available data point at baseline and 3-months. Therefore, body mass index (BMI) is our primary health outcome and will be calculated based on CDC growth charts using height and weight.

4.4.2 Demographics Survey will be used to collect parent and family demographics (e.g. annual household income, education-levels, family's medical history) from parents of study participants (n=50) at baseline. The survey will be sent electronically using REDCap to give the parent the option of completing the survey prior to the clinic visit. Alternatively, the parent may complete the questionnaire while in the waiting room at the clinic.

4.4.3. Health Behavior & Attitudes Survey will be used to collect physical activity and nutrition behaviors and attitudes from adolescent patients (n=50) at baseline and follow-up. This information will be used to populate the PREVENT tool's risk profile and determine changes in physical activity and nutrition behaviors and attitudes from baseline to post-intervention. The physical activity questions are adapted from the International Physical Activity Questionnaire (IPAQ) that has been validated for use in adolescents.^{42,43} Nutrition questions are generated based on the Stoplight Diet³⁸ for adolescents and the Rapid Eating Assessment for Participants - Shortened Version.⁴⁴ Attitudes toward behavior change questions were adapted from two validated surveys: 1) ⁴⁵⁻⁴⁷the Treatment Self-Regulation Scale ^{48,49} and 2) the Rapid Eating Assessment for Participants - Shortened Version.⁴⁴

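### The change-from-baseline regression gives up precision that a baseline-adjusted analysis keeps, and it drops any randomised patient who has a valid follow-up record but no valid baseline (plausible mainly for accelerometry)

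*Combined protocol and SAP*

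**What the plan says.** Section 2.0 plans for "Fifty adolescents aged 12 to 19 years at risk for poor CVH", "randomized to intervention or wait-list control". The allocation ratio is not stated.

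The only between-arm test for Aim 2 is in Section 5.2: "Change from baseline between study groups will be tested using linear regressions". The threshold follows: "Statistical significance will be defined as p<0.05". Section 5.2 names no covariates, analysis set or rule for missing values.

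Four other places bear on who has a baseline value:

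- Section 4.2.1, on sequence: "Following baseline measurement, patients will be randomized to intervention or wait-list control and attend their clinic visit". No section makes a complete or valid baseline a condition of randomisation.
- Section 4.2.1, on a staff call one week before the visit, partly to "address any barriers they may be facing to complete baseline measurements".
- Section 4.4.4, on the baseline accelerometer, which is "returned by mail using a provided prepaid envelop or at the clinic visit". The same section lists an intervention-arm document alongside the contents of the baseline device mailing.
- Section 4.4.3, on the baseline survey: "This information will be used to populate the PREVENT" tool's risk profile.

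**The concern.** A change score exists only when both values exist. A device handed in at the clinic visit cannot have been checked for adequate wear before randomisation, because the visit comes after it. A patient can therefore be randomised, turn out to have no usable baseline week, and still give a good 3-month record. The stated regression cannot use that record. Adding baseline as a covariate in an ordinary complete-case regression improves precision, but drops the same patient.

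Separately, an unadjusted change score uses the baseline inefficiently even when nobody is missing. With 50 patients, both losses widen the interval around the Aim 2 arm comparison, although the follow-up data have been collected.

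**Working it through.** The documents state no power, SD, correlation or missing-data rate, so there is no planned figure to reproduce. The size has to be shown over assumed values.

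**Inputs.** From the documents: 50 patients, two arms, change-score regression. Assumed: 25 per arm; equal SD (set to 1) at both times; baseline-to-follow-up correlation ρ of 0.4, 0.6 or 0.8; 20% of follow-up records unusable; 10% or 20% of baseline records unusable, independently and at random.

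**Numbers per arm.** Let c be patients with both records and f those with follow-up only.

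- 10% of baselines unusable: c = 25 × 0.9 × 0.8 = 18; f = 25 × 0.1 × 0.8 = 2.
- 20% of baselines unusable: c = 25 × 0.8 × 0.8 = 16; f = 25 × 0.2 × 0.8 = 4. Over both arms, 32 patients have pairs and 40 have a 3-month value.

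**Variance of the arm difference** (large-sample, variances treated as known, equal numbers per arm):

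- Unadjusted change score on pairs: 4(1 − ρ)/c
- Baseline-adjusted regression on pairs: 2(1 − ρ²)/c
- Repeated-measures model with common baseline mean: 2/[c/(1 − ρ²) + f]

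**Step 1, adjustment alone.** Adjusted over change score is (1 + ρ)/2, which is 0.70, 0.80 and 0.90. It does not depend on how many baselines are missing.

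**Step 2, recovered patients alone.** Constrained model over adjusted regression is c/[c + f(1 − ρ²)].

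| Baselines unusable | ρ = 0.4 | ρ = 0.6 | ρ = 0.8 |
|---|---|---|---|
| 10% | 18/(18 + 2×0.84) = 0.915 | 18/(18 + 2×0.64) = 0.934 | 18/(18 + 2×0.36) = 0.962 |
| 20% | 16/(16 + 4×0.84) = 0.826 | 16/(16 + 4×0.64) = 0.862 | 16/(16 + 4×0.36) = 0.917 |

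The gain from recovered patients is thus 4-9% of variance at 10% and 8-17% at 20%. In standard error this is about 2-4% and 4-9%.

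**Step 3, both together at 20%.** 0.70 × 0.826 = 0.58; 0.80 × 0.862 = 0.69; 0.90 × 0.917 = 0.83. Adjustment accounts for 0.30 of the 0.42 reduction at ρ = 0.4, 0.20 of 0.31 at 0.6, and 0.10 of 0.17 at 0.8: more than half each time.

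**Simulation check.** With 3000 trials per scenario at 20%/20%, the constrained model's variance was 0.60/0.70/0.85 of the change score's and 0.80/0.85/0.91 of the adjusted regression's. All three estimators were unbiased.

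**Cost of the constraint.** Suppose knowing the allocation shifts one arm's baseline by 0.2 SD with no true effect, with 22 pairs and 3 follow-up-only per arm and ρ = 0.7. The constrained model's bias has size 0.7 × 0.2 × 22/(22 + 3×0.51) = 0.13 SD; its SE is √(2/(22/0.51 + 3)) = 0.208, and type I error is about 0.10. The change score carries the whole 0.20 SD as bias.

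**The case against.** **The missing-baseline rate is assumed.** Baseline is meant to come before randomisation, and the reminder call is there to prevent gaps. This stands. If only one of 25 per arm lacks a baseline and no follow-up is lost, the gain from recovery is about 1-4% of variance (ρ from 0.9 down to 0.3).

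**Section 5.2 does not exclude baseline as a covariate.** This stands too. If the regression already adjusts for baseline, the step 1 gain disappears from the criticism and only step 2 remains. A reader might credit the whole step 3 reduction to recovered patients; the arithmetic does not support that.

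**Surveys are hardly affected.** The tool needs the baseline survey, and the device-return argument does not apply to it. A reader who carries the 20% scenario over to surveys goes beyond the documents.

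**Other methods also keep these patients.** In a 6000-run simulation at 20%/20%, mean-imputing the baseline with a missing-value indicator gave variances of 0.83 and 0.88 of complete-case adjustment at ρ = 0.4 and 0.6, but 1.09 at 0.8. The proposed model is therefore a reasonable choice rather than the only one.

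**The remedy is not free.** It assumes values missing at random and equal baseline means by randomisation. Section 4.4.4's arm-specific document suggests that allocation may be known before baseline wear, contrary to Section 4.2.1. This puts the constraint in doubt for the very outcome where baselines are most likely to be missing. It does not rescue the planned analysis, which such a shift biases more.

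**Conclusion.** The point holds as one about precision. As written, the change-score regression is less efficient than a baseline-adjusted analysis (variance ratio 0.70 to 0.90 in favour of adjustment) and cannot use follow-up-only patients. Recovering them adds 4-9% in variance at 10% unusable baselines and 8-17% at 20%. These figures rest on 25 per arm, 20% of follow-up unusable, equal SDs, ρ of 0.4 to 0.8 and values missing at random.

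Two stronger readings are tempting. A reader might infer that analysing only patients with pairs biases the comparison; no document shows this, and the simulation was unbiased under its assumptions. A reader might also infer that survey and accelerometer effect estimates will set the design of the larger trial. Section 5.2 says only that the integrated findings will shape an implementation strategy for it, and Section 4.4.1 names BMI as the primary health outcome.

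In a 50-patient feasibility study with no power target, this is an optional improvement, worth making because it is cheap.

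**What to change.** For survey and accelerometer outcomes, replace the change-score regression in Section 5.2 with one repeated-measures model in SAS PROC MIXED:

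- two times, baseline and 3 months;
- one common baseline mean for both arms, with an arm effect at 3 months only, which is the treatment effect;
- unstructured covariance and Kenward-Roger degrees of freedom;
- every randomised patient with at least one value included.

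Report by arm the numbers with pairs, baseline only and follow-up only. That count is itself a feasibility result. State the missing-at-random and equal-baseline assumptions.

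Before applying the constraint to accelerometry, reconcile Section 4.2.1 (randomisation after baseline) with Section 4.4.4 (intervention-arm document listed with the baseline device mailing). Section 4.4.4 also gives a 6-month accelerometer follow-up where Sections 2.0, 4.2.1 and 4.3.1 give 3 months; settle this too, since the model needs a single follow-up time.

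The cost is one paragraph of analysis text and a few lines in software already named, with no new data or patients. The downsides are the two assumptions and a slightly less familiar model. The change does not address missing 3-month EHR values, which are a separate problem.
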